5. TREATMENT OF SUBJECTS

5.1 Investigational product/treatment

Automated control of the FiO₂ based on the measured SpO₂ during 8 hours. The algorithm, named PRICO, that is used to control the FiO₂ is integrated into the Fabian HFO ventilator (Acutronic Medical GmbH, Hirzel, Switserland) and has a CE certificate. Saturation data is fed into the system through an integrated Masimo (Irvine, USA) pulse oximeter. For this purpose an additional pulse oximeter sensor is placed on of the infants extremities during the automated control of the FiO₂.

5.2 Use of co-intervention (if applicable)

Not applicable

5.3 Escape medication (if applicable)

Not applicable

6. INVESTIGATIONAL PRODUCT

6.1 Name and description of investigational product(s)

Predictive intelligent control of oxygenation (PRICO) a closed loop algorithm that adjust the fraction of inspired oxygen (FiO₂) based on the oxygen saturation measured by pulse oximetry (SpO₂). This algorithm is integrated into the Acutronic Fabian HFO (Acutronic Medical GmbH, Hirzel, Switzerland) neonatal ventilator. This ventilator is equipped with its own Masimo Setline (Masimo Corporation, Irvine, USA) pulse oximeter. Both these devices are CE certified.

6.2 Summary of findings from non-clinical studies

When twenty two preterm lambs were ventilated with the PRICO closed loop algorithm, the time within the SpO₂ target range (90-95%) significantly better than manual control [20].

Animals were stabilized within the first half hour of life (median 33:11 min:sec, IQR (30:01–39:47 min:sec)). During the subsequent stable ventilation phase, time spend within the target range was significantly higher when the automated controller was used (93.2% (80.6–98.9%) vs. 84.0% (63.8–89.4%), P < 0.05, Figure 3a), and time outside the target range, depicted as area under the curve (SpO₂*sec per hour) was significantly lower (Figure 3a). The number of episodes outside the target range per hour was also significantly lower in the automated group (Table 3).

When comparing hypoxic and hyperoxic episodes, animals ventilated with automated control had significantly less episodes below the lower target saturation of 90% and showed a trend toward less hyperoxic episodes per hour (P = 0.065, Table 3). We observed only a small number of short hypoxic (<85%) and severe hypoxic (<75%) episodes in our model, and number of these episodes did not differ between groups. This was also reflected in the low average deviation of saturation from the median target saturation in both groups (Table 3). The duration of hyperoxic, hypoxic and severe hypoxic episodes did not differ significantly between groups.

Compared to manual control, the number of FiO_2 adjustments per hour was 2.3 times higher in the automated group, although this difference was not significant (median 13.0, IQR (3.0– 16.4) vs. 5.7 (2.3–9.8), P = 0.243). Applied FiO_2 did not differ significantly between groups, and we observed a heterogeneous need for oxygen within the groups (Figure 3b). Animals in the manual group were outside target range longer with higher oxygen need, however correlation between time outside target range and average FiO_2 was not significant (R² linear = 0.614, P = 0.889). In the automated group, average FiO_2 and time outside target range did not correlate (R² linear = 0.229, P = 0.136).

This algorithm has only been tested on intubated animals. Due to the mandatory sedation these animals have no respiratory drive of their own, so synchronised and non-invasive ventilation cannot be tested.

From this trial we speculate that in a clinical scenario where not only SpO₂ but also clinical evaluation of the patient influence oxygen therapy, the combination of automated and manual control might even imply better results.

6.3 Summary of findings from clinical studies

PRICO the algorithm developed within the Erasmus MC has not yet been tested during a clinical trial.

Other automatic "closed loop" system for regulation of FiO₂ based on SpO₂ have been used during several clinical trials. Different devices have proven the feasibility of automated closed loop FiO₂ control in the NICU for various modes of ventilation, mixed populations, and by using different algorithms [13, 16, 21-25]. Different algorithms have been tested on different patient groups consisting of both intubated an non intubated patients, receiving different ventilation modes. In addition, an overall reduction of manual interventions during automated control was found in these studies, indicating facilitation of caretakers and nursing staff in clinical routine [26, 27]. However, at least one study raised concerns about safety, as time within target range was accompanied by an increase in time spent below target range [16]. Only high frequency ventilation has not yet been tested. Why is unclear, but might be due to the limited number of devices that are available on the market. From an engineering and physiological standpoint this mode should behave just as well or better than normal mechanical ventilation given through an endotracheal tube.

6.4 Summary of known and potential risks and benefits

There are no known potential risks.

The benefit shown in pre-clinical trials include an improvement of the time spend within the oxygen saturation target range, a reduction in both hyper and hypoxia.

6.5 Description and justification of route of administration and dosage

6.6 Dosages, dosage modifications and method of administration

6.7 Preparation and labelling of Investigational Medicinal Product

6.8 Drug accountability

7. NON-INVESTIGATIONAL PRODUCT

Not applicable

- 7.1 Name and description of non-investigational product(s)
- 7.2 Summary of findings from non-clinical studies
- 7.3 Summary of findings from clinical studies
- 7.4 Summary of known and potential risks and benefits
- 7.5 Description and justification of route of administration and dosage
- 7.6 Dosages, dosage modifications and method of administration
- 7.7 Preparation and labelling of Non Investigational Medicinal Product
- 7.8 Drug accountability

8. METHODS

8.1 Study parameters/endpoints

8.1.1 Main study parameter/endpoint

The main study parameter is the oxygen saturation measured with a pulse oximeter (SpO_2) . The goal is to stay within the SpO_2 target range. The range is dependent on the gestational age (GA) of the neonate:

 Table 1: Oxygen saturation targets form the Erasmus MC - Sophia (2015)

-	Prematuren <37 weken met zuurstoftoediening	89-95%
-	Prematuren <37 weken met NO-toediening	92-98%
-	A term neonaten met zuurstoftoediening	92-96%
-	A term neonaten met NO-toediening	92-98%

The main parameter is the area outside of the SpO_2 target range. This gives an indication of both the time outside of the target range as well as the deviation from the target. The number of times the SpO_2 is above and or below the target range is logged, as is the duration of the event and the average deviation from the target.

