An observational study conducted on our Neonatal Intensive Care Unit (NICU) has shown that infants on average spend only 54% of the time within the SpO_2 limits and 71 adjustments to the FiO₂ are made each day.

An automated controller (PRICO) has been developed that adjusts the FiO₂ based on the SpO₂. A study in a preterm lamb model has shown the effectiveness of this closed loop controller: less periods of desaturation and hyperoxia were demonstrated.

Objective: To test the safety and feasibility of a closed loop controller of the FiO_2 based on the measured SpO_2 in a NICU setting.

Study design: Neonates that are included will start with an 8 hour block of manual adjustment of the FiO₂. After completion of this block they will be switched to the automated control of the FiO2 for another 8 hours. After that they are switched back for another 8 hours of manual control, which is used to correct for any changes of the state of the neonate during the trial. For each ventilation type (high frequency , invasive and non-invasive) 24 patients will be included.

Study population: Neonates admitted to the NICU in the Erasmus MC, Rotterdam and Máxima Medical Centre, Veldhoven that are receiving respiratory support and a FiO_2 of more than 21%.

Intervention (if applicable): Automated control of the FiO₂ based on the measured SpO₂ during 8 hours.

Main study parameters/endpoints: The main parameter during the study is the time the SpO₂ spend within the target range. Secondary outcomes are the number of hyper and hypoxic events, average maximum and minimum SpO₂ during these events, number of FiO₂ adjustments (manual and automated) and cerebral oxygen saturation.

Nature and extent of the burden and risks associated with participation, benefit and group relatedness: There is no burden to the patient, and the risk is minimal. The same patient monitoring is used during the study as during routine care. The closed loop

algorithm is implemented in to the Acutronic Fabian HFO ventilator, so that no additional equipment is needed at the bedside.

The controller is designed so that it checks the input signals, the validity of the pulse oximetry and the quality of the ventilation. If any of the checked parameters is not within the specified limits the controller will not adjust the FiO_2 and give an alarm.

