2. OBJECTIVES

Primary Objective: To test the safety and feasibility of a closed loop controller of the FiO_2 based on the measured SpO_2 in a NICU setting. This is determined by the time spend within the SpO_2 target range, and the number of times the SpO_2 was above and below the target.

Secondary Objective(s):

Track the usage of the fraction of inspired oxygen (FiO₂) during the periods. A higher oxygen use is only acceptable when it results in an improvement of the time spend within the oxygen saturation target range without a rise in hyperoxia. In all other cases a lower FiO_2 is preferred.

The respiratory support is analysed, to see if any changes were made to the ventilation settings. Changes to the pressure or timing can influence the need for additional oxygen.

Reduction in manual FiO_2 adjustments. Although the FiO_2 is adjusted automatically, it is still possible to adjust the FiO_2 by hand. This can be done on clinical indication. For example before an alteration to the respiratory support is made, before suctioning, or before respiratory support is halted for another reason.

[figure not shown]
When the infants are monitored with near infrared spectroscopy (NIRS) to monitor their cerebral oxygenation, this data will be analysed in order to see if automated oxygen control improves the stability of their cerebral oxygenation.

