4.4 Sample size calculation

The sample size calculation is based on the area under the curve for the SpO_2 . Giving a value that has a unit of [% SpO_2 *min]. A value of 30 can be reached by a SpO_2 of 30% outside of the target during 1 minute, or 30 minutes a SpO_2 that is 1% outside of the target. Values are normalized per hour.

During the animal trial conducted with this algorithm a reduction in the average of the area under the curve was found from 21 to 3 [%SpO₂*min per hour], with a standard deviation of 30 [%SpO₂*min per hour]. We accepted a significance level of 5% and a power of 80%. Because of the study design, each patient is its own control. Because of that only 22 patients are needed (Stata, StataCorp LP, USA). Because we want to show that the algorithm works in all 3 strata of ventilation we need three groups of 22 patients, and we expect a 10% dropout rate due to withdrawal or improvement in ventilation up to the point that additional oxygen is no longer needed, resulting in a total sample size of 72 patients.

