10.1 Primary study parameter(s)

The efficiency of the PRICO algorithm will be assessed by comparing the time spend outside and deviation from the SpO₂ target range. This is done with the area under the curve, normalized to a one hour period [SpO₂*min per hour]. It is calculated by taking the SpO₂ value from the patient monitor, logged once every second and, when it is outside the SpO₂ target range, subtract the target. The absolute value of all deviations is added together and divided by the length of all the recorded data in hours. The significance will be tested with a repeated measurement ANOVA.

The number of collected data points per period will be reported to show any possible bias due to unmeasurable SpO₂ levels, malfunctions or other events. This will be reported as a percentage of time recorded.

When there is a significant difference between the first and last period, the argument will be made that the patient changed overtime. In that case the automated period will be compared with the best of the two observational periods.

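### The Summary and the Objectives name a different primary endpoint from the one that is sized, defined and tested; separately, the written area formula is 60 times its labelled unit

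*Protocol*

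**What the plan says.** Three statements of the main outcome stand in the protocol.

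- **Summary:** "The main parameter during the study is the time the SpO₂ spend within the target range". Numbers of hyperoxic and hypoxic events are listed there as secondary.
- **Section 2, primary objective:** safety and feasibility are to be judged by "the time spend within the SpO_2 target range, and the number of times the SpO_2 was above and below the target". The area is not mentioned, and the counts now belong to the primary objective.
- **Section 8.1.1:** "The main parameter is the area outside of the SpO_2 target range".

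Two further sections follow 8.1.1. Section 4.4 says "The sample size calculation is based on the area under the curve for the SpO_2". Section 10.1, on the primary parameter, compares time outside range and deviation from it and adds "This is done with the area under the curve, normalized to a one hour period".

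On computing the area, 10.1 takes SpO2 values "logged once every second and, when it is outside" the range, subtracts the target, and continues: "The absolute value of all deviations is added together and divided by the length of all the recorded data in hours". The unit given in 10.1 is SpO2·min per hour. Section 4.4 uses %SpO2·min per hour for the animal planning figures, whereas Section 6.2 describes the animal area in SpO2·sec per hour.

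**The concern.** A reader of the Summary or the Objectives would expect the trial to be decided on time in range, with or without episode counts. A reader of 4.4, 8.1.1 and 10.1 would expect the area. No text says which prevails if they differ, or how the counts bear on the primary conclusion. The study is neither randomised nor blinded, so the primary outcome needs to be settled in writing beforehand. If it is not, a favourable result on any of these measures could be presented as the primary result with some support from the protocol, and only one of them has a sample size behind it.

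The area formula is a separate and smaller matter. Followed literally, it gives values on a different scale from the planning figures.

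**Working it through.** **1. The plan's own sample size.** Inputs from 4.4: means 21 and 3, so a difference of 18; SD 30; significance level 5%; power 80%; each patient as own control. Taking 30 as the SD of the within-patient difference and a two-sided test:

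n = (SD × (1.960 + 0.842) / difference)² = (30 × 2.802 / 18)² = 21.8, so 22 per stratum, as stated.

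The calculation uses the area only. The protocol gives no planning difference or SD for time in range or for episode counts.

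**2. Whether the measures can disagree.** Section 4.4 gives two ways to reach an area of 30 in an hour:

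| Pattern | Area (%·min) | Time in range |
|---|---|---|
| 30% outside for 1 min | 30 × 1 = 30 | 59/60 = 98.3% |
| 1% outside for 30 min | 1 × 30 = 30 | 30/60 = 50% |

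The same area therefore covers very different times in range. A reversal is also possible. The values in this illustration are invented, not taken from the protocol:

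| Hypothetical hour | Area (%·min) | Time in range |
|---|---|---|
| Manual: 1% outside for 30 min | 30 | 50% |
| Automated: 15% outside for 3 min | 45 | 57/60 = 95% |

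Time in range favours automation and the area favours manual control.

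**3. Cost of a free choice between two measures.** Two test statistics are taken as bivariate normal with no true effect, each tested at |z| > 1.96. The protocol gives no correlation between the measures, so a range is assumed.

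| Assumed correlation | Either significant, two-sided | Either significant in favour of automation |
|---|---|---|
| 0.5 | 9.1% | 4.5% |
| 0.9 | about 7.0% | 3.5% |
| Single endpoint | 5% | 2.5% |

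**4. The area formula.** The formula in 10.1 is the sum of absolute deviations over 1-second samples, divided by recorded hours. Applied to the 4.4 examples in a one-hour record:

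- 30% for 1 min: 60 samples × 30 = 1,800; divided by 1 hour = 1,800.
- 1% for 30 min: 1,800 samples × 1 = 1,800; divided by 1 hour = 1,800.

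Section 4.4 gives 30 for both. The ratio is 1,800/30 = 60, the number of seconds in a minute. On the literal scale the planning values 21, 3 and 30 would be 1,260, 180 and 1,800. The sample size does not move, because 1,080/1,800 = 18/30 = 0.6. A repeated-measures ANOVA on simulated data gave the same result before and after multiplying by 60 (F = 0.725, p = 0.490 both times).

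**The case against.** The strongest reply is that the operative sections agree. Sample size, endpoint definition and primary analysis all use the area, and 10.1 attaches one test to it. Sections 8.1.1 and 10.1 also present the area as the way in which time outside range and depth of deviation are captured together. On this view the Summary line and the general objective are loose wording, and reporting anything else as primary would visibly depart from three sections. This stands as a reason to choose the area as the single endpoint. It does not remove the contradiction: Section 2 states what decides the primary objective and omits the area, and no sentence gives 8.1.1 or 10.1 precedence.

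A second reply concerns the size of the error inflation. The correlations are assumed, and the two-sided figures count results favouring manual control as well. Both points are right, and for that reason the one-directional figures are shown beside the two-sided ones.

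Two stronger readings are tempting and should be resisted. A reader might infer a free choice among four measures (time, area, counts above, counts below), with still larger inflation. Section 2 does not offer that: it joins time in range and the counts with "and". If all had to succeed, false positives would fall and power would become the difficulty. A reader might also infer that the factor of 60 helps to leave success undefined. It does not. A constant multiplier changes no p-value, the label in 10.1 and the example in 4.4 make the intended unit plain, and dividing by 60 restores comparability.

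Finally, the example in 4.4 shows that the measures can part company, not how often they would in these infants. That remains unknown.

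**Conclusion.** The contradiction is real, and it lies between the Summary and Section 2 on one side and Sections 4.4, 8.1.1 and 10.1 on the other. The Summary and Section 2 also differ from each other on whether episode counts are secondary or part of the primary objective. Only the area is supported by the stated 22 patients per stratum. If the sponsor could choose between two of the measures, the false-positive risk would rise modestly, to the levels in step 3. Those levels rest on assumed correlations of 0.5–0.9 and a normal approximation.

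The formula in 10.1 is also wrong as written, by a factor of exactly 60. Its effect is confined to the reported values and their comparison with 21, 3 and 30. The differing units for the animal area in 6.2 and 4.4 should be checked for the same reason; the sample size is unaffected provided that 21, 3 and 30 share one unit.

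**What to change.** - Name the hourly area outside the target range as the sole primary endpoint in the Summary and in Section 2, to match 4.4, 8.1.1 and 10.1.
- List time in range, and the counts above and below range, as secondary endpoints wherever endpoints are described.
- In 10.1, divide the summed 1-second deviations by 60 before dividing by recorded hours.
- Confirm against the source data which unit the animal figures carry, and use that unit consistently in 6.2 and 4.4.

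These are text amendments. They need no extra patients or data and no change of test. Making time in range primary instead would cost more, because the calculation in 4.4 would have to be redone with planning values for that measure.

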8.1.2 Secondary study parameters/endpoints (if applicable)

The other important parameter is the fraction of inspired oxygen (FiO_2). Although it is acceptable to have a higher FiO2 during a period, this is only acceptable if it results in an significant improvement in the time spend within the target range, and not cause a significant rise in the time spend above the target range.

The number of manual changes of the FiO2 are logged during both routine and

automated control. And the number of times that the PRICO algorithm disables

due to insufficient ventilation or problems with the pulse oximeter are logged.

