1. INTRODUCTION AND RATIONALE

Supplemental oxygen is given to preterm infants to ensure that they have an adequate arterial saturation (SpO₂), and is one of the most common therapeutic interventions in the neonatal intensive care unit (NICU) [1]. Fluctuations in the SpO₂ are dealt with by adjusting the fraction of inspired oxygen (FiO₂), a challenging and time consuming task. During the recovery of a desaturation there is often an overshoot, resulting in a period of hyperoxia. Both hypoxia and hyperoxia must be avoided because of their detrimental effects on morbidity and mortality in these children. While hypoxia may lead to direct and indirect cellular damage, hyperoxia has been associated with oxygen toxicity, oxidative stress [2], and chronic diseases of preterm infants such as bronchopulmonary dysplasia (BPD) [3] and retinopathy of prematurity (ROP) [4]. And there is growing evidence that hyperoxia may be equally damaging to the developing brain.

Large deviations from SpO₂ targets during routine NICU care of preterm infants have been observed in clinical observational studies, where SpO₂ target ranges are met during 50% of the time, and 71 adjustments to the FiO₂ are made each day. [5, 6]. Meeting SpO₂ targets affects morbidity and mortality, depending on the target range chosen [7-9]. Beside overall SpO₂ targets, variability of oxygenation influences outcome of preterm infants [4, 10, 11]. A promising solution to optimize oxygen therapy is the employment of an automatic "closed loop" system for regulation of FiO₂ based on SpO₂. Several clinical trials with different devices have proven feasibility of automated closed loop FiO₂ control in the NICU for various modes of ventilation, mixed populations, and by using different algorithms [5, 12-17]. In addition, an overall reduction of manual interventions during automated control was found in these studies, indicating facilitation of caretakers and nursing staff in clinical routine [18, 19]. However, at least one study raised concerns about safety, as time within target range was accompanied by an increase in time spent below saturation target range [16].

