10.2 Secondary study parameter(s)

The FiO₂ administer during the three different periods of the study is tested a repeated measurement ANOVA. Additional oxygen is only exactable when it results in a significant improvement in the stability of the SpO₂.

Manual FiO_2 changes are compared, and data is analysed to check for the reason of manual intervention during the automated FiO_2 period. Periods when the algorithm is turned off are reported, both in length, total period and average duration per period and total number of times that the algorithm was stopped. Normally the algorithm turns of when there are problems with either the SpO₂ measurement or the ventilation.

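### The primary AUC pools deviations below and above target and Section 10 compares neither direction, so a significant fall could coexist with more hypoxic area; separately, 8.1.2 rests on a non-significant rise in time above target

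*Protocol*

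**What the plan says.** Section 2 makes safety and feasibility the primary objective, judged by time in the target range and "the number of times the SpO_2 was above and below the target".

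Section 8.1.1 names the area outside the range as the main parameter, and section 10.1 fixes its formula: "The absolute value of all deviations is added together and divided by the length of all the recorded data in hours". The result is tested by repeated-measures ANOVA. Section 10 contains no comparison of area, time or episodes below target, or of the same quantities above target.

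On known risks, the introduction reports that in at least one earlier closed-loop study "time within target range was accompanied by an increase in time spent below saturation target range"; section 6.3 repeats this. Section 13.2 gives overshoot into hypoxia or hyperoxia as the largest residual risk.

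A condition on higher oxygen use appears in three forms:

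- Section 2 wants better "time spend within the oxygen saturation target range without a rise in hyperoxia".
- Section 8.1.2 says of a higher FiO2 that "this is only acceptable if it results in an significant improvement in the time spend within the target range", and that it must "not cause a significant rise in the time spend above the target range".
- Section 10.2 asks only for a "significant improvement in the stability of the SpO"2, with no condition on hyperoxia.

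**The concern.** A sum of absolute deviations has no direction. If automation removes much hyperoxic area and adds some hypoxic area, the primary outcome improves and the added hypoxia does not show in it. The protocol itself reports more time below range as a safety concern with closed-loop control, so a trial whose primary objective is safety should be able to show that component with its uncertainty.

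Episode counts do not fill the gap. Fewer but longer or deeper desaturations would lower the count while time or area below target rose.

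The second matter concerns the other direction. Section 8.1.2 treats a rise in time above target as acceptable unless it is statistically significant. In a small sample, failing to reach significance is weak evidence that there was no rise.

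**Working it through.** **Inputs.** Section 4.4 gives a mean AUC of 21 under manual and 3 under automated control (lamb study), SD 30, alpha 5%, power 80%, 22 patients per ventilation stratum, three strata, 72 in total. Assumptions: the SD is that of within-patient differences, tests are two-sided, and a paired t-test stands in for the automated-versus-manual contrast of the repeated-measures ANOVA.

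**The plan's own figure.** n = (SD × (1.960 + 0.842) / difference)² = (30 × 2.802 / 18)² = 21.8, so 22. The stated figure reproduces under these assumptions. Adding 10%: 22 × 1.1 = 24.2, taken as 24, and 3 × 24 = 72.

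**Fall in pooled AUC needed for significance.** Required fall = t(0.975, n−1) × SD / √n.

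- n = 22: 2.080 × 30 / √22 = 13.3. The automated total must be at most 21 − 13.3 = 7.7.
- n = 66 (strata pooled): 1.997 × 30 / √66 = 7.4. The automated total must be at most 13.6.

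**When hypoxic area can rise all the same.** If the total falls by F while the below-target part rises, the above-target part must fall by more than F. It must therefore have exceeded F under manual control.

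- n = 22: manual share above target greater than 13.3 / 21 = 63%.
- n = 66: greater than 7.4 / 21 = 35%.

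Illustrations with assumed splits of the manual 21, with hypoxic area doubling and hyperoxic area removed:

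| Manual (below + above) | Automated (below + above) | Fall in total | At least 13.3 (n = 22)? | At least 7.4 (n = 66)? |
|---|---|---|---|---|
| 3 + 18 | 6 + 0 = 6 | 15 | yes | yes |
| 5 + 16 | 10 + 0 = 10 | 11 | no | yes |
| 10.5 + 10.5 | 21 + 0 = 21 | 0 | no | no |

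Masking is therefore possible, but only with a suitable split. With an even split, doubling hypoxic area cancels the whole gain.

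**Strength of the non-significance condition in 8.1.2.** The protocol gives no SD for time above target, so the true rise is put in SD units of the paired difference. This is the probability that a paired t-test at two-sided 5% flags the rise (noncentral t):

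| True rise | n = 22 | n = 66 |
|---|---|---|
| 0.2 SD | 14% | 36% |
| 0.3 SD | 27% | 67% |
| 0.5 SD | 61% | 98% |

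With 22 infants, a true rise of 0.3 SD goes unflagged in 100 − 27 = 73% of trials. These figures concern time above target and say nothing about hypoxia.

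**The case against.** Hypoxia is not ignored. The summary lists hypoxic and hyperoxic events, with the average extreme SpO2 in each, as secondary outcomes. Section 2 puts the counts inside the primary objective. Section 8.1.1 logs number, duration and mean deviation, from which area below target could be rebuilt. A statistical analysis plan, which is not at hand, may specify the comparison. In lambs (section 6.2) automated control gave significantly fewer episodes below 90%. Section 8.7 halts the study when staff report fluctuation around the target or failure to bring saturation into range, in either direction.

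Much of this stands. A rise in hypoxia could be seen descriptively, and an unlisted test alone would be no finding. But the protocol itself fixes the pooled formula and the significance wording. It names counts rather than time or area below target, and the halting rule sets no numerical limit on hypoxia.

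A reader might infer that 8.1.2 would let PRICO be declared safe while hypoxia increased. The documents do not support that. The condition applies only when FiO2 is higher, for which time above target is the natural harm, and nothing says that meeting it establishes safety. It also requires a significant gain in time within range. Since times below, within and above range sum to 100%, time below could then rise only if time above fell by more than that gain, which is hard to reconcile with higher FiO2. The weak significance condition and the pooled AUC are two separate matters.

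**Conclusion.** The point holds as a worthwhile, inexpensive improvement. The primary AUC cannot show which side of the target changed, and Section 10 fixes no directional comparison for a trial whose first objective is safety. On the protocol's own figures, a significant fall could hide a rise in hypoxic area only if manual control is mainly hyperoxic: more than about 63% of the area with 22 infants, or about 35% with 66 pooled. The actual split is unknown, the AUC of 21 comes from lambs, and the SD of 30 is taken as that of the paired differences. This shows that masking is possible, not that it is likely.

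Separately, the non-significance wording in 8.1.2 is a weak guard against more time above target: 27% detection of a 0.3 SD rise with 22 infants and 67% with 66, in assumed SD units. Sections 2, 8.1.2 and 10.2 also state the condition in three different ways.

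**What to change.** Keep the pooled AUC as the primary outcome. Add to Section 10, as named safety outcomes, the area below target, area above target, time below target and time above target. Compute them from the same second-by-second SpO2 record and give each the automated-minus-manual difference with a 95% confidence interval. Base any statement that time or area did not rise on that interval, not on a non-significant p-value.

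Reconcile the wording in Sections 2, 8.1.2 and 10.2. Whether to set a margin or any clinical criterion is for the investigators.

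The cost is a few sentences of protocol text and a little more analysis, with no extra patients or measurements. The trade-off is that a safety statement becomes harder to claim, because the intervals may be wide with 22 infants per stratum.
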